#### **5.3.1 Laboratory Test Assessments**

A local laboratory will perform the analysis and will provide reference ranges for these tests. Results of clinical laboratory tests should be available for review prior to dosing on Day 1 of each treatment cycle. For other visit days, laboratory tests results should be reviewed within 24 hours of the visit. With the exception of laboratory assessments prior to the first dose of panobinostat/Ipilimumab, all laboratory tests can be performed within 24 hours prior to the scheduled visits. Laboratory assessments prior to the first dose of panobinostat/Ipilimumab may be performed up to 72 hours prior to the scheduled visits.

The following clinical laboratory tests will be performed:

#### **Hematology**

Hemoglobin Hematocrit Total leukocyte count, including differential Platelet count

#### **Serum Chemistry**

Aspartate aminotransferase (AST) Alanine aminotransferase (ALT) Total bilirubin Direct bilirubin, if total bilirubin > ULN Alkaline phosphatase

Lactate dehydrogenase (LDH) Creatinine Blood Urea Nitrogen (BUN) or Urea Amylase Lipase

**Serology**

Uric Acid Glucose Total Protein Albumin Sodium Potassium Chloride Calcium Phosphorus Magnesium Bicarbonate; HepB, HepC, HIV (at screening only)

**Other Assays**

T4/TSH

**Urinalysis**

Protein Glucose Blood Leukocyte esterase Microscopic examination of the sediment if blood, protein or leukocyte esterase are positive on the dipstick

**Coagulation Profile**

PT/INR aPTT

**Other Analyses**

Pregnancy test (WOCBP only) FSH (if needed to document post-menopausal status as defined in Section 3.3.3)

At the investigator’s discretion, laboratory tests may be repeated if clinically significant. If the units of a test result differ from those printed on the CRF, the recorded laboratory values must specify the correct units. Any abnormal laboratory test result considered clinically significant by the investigator must be recorded on the appropriate AE page of the CRF (see Section 6.2 Laboratory Test Abnormalities).

**5.4 Efficacy Assessments**

In this study, immune-related Response Criteria (irRC; see Appendix 4) will be used to assess subject response to study treatment and guide clinical care. However, response- based assessments in this study will be captured using both modified irRC and RECIST 1.1. The investigator will determine the irRC response at each tumor assessment. The RECIST 1.1 response for the patient will be calculated from the tumor assessment data by the Sponsor and will be used for reporting purposes. The RECIST 1.1 criteria will be used to determine subjects’ best overall response (BOR), and for statistical analysis of efficacy in this study. Assessments of tumor status will be made during screening and then at 6 and 12 weeks and then every 12 weeks thereafter. The irRC represent modifications of the modified WHO criteria reflecting the clinical experience with ipilimumab in the completed and/or ongoing clinical studies in which objective and durable responses (as per mWHO) were observed in subjects following progression and without intervening alternative anti-cancer therapy. As such, the irRC are designed to capture clinical activity of ipilimumab immunotherapy that may not be adequately addressed by the RECIST 1.1 criteria and will only be used for patient management decisions, not formal efficacy reporting.

[REDACTED]

[REDACTED]

[REDACTED]

[REDACTED]

[REDACTED]

[REDACTED]

## 6 ADVERSE EVENTS

An *Adverse Event (AE)* is defined as any new untoward medical occurrence or worsening of a pre-existing medical condition in a patient or clinical investigation subject administered an investigational (medicinal) product and that does not necessarily have a causal relationship with this treatment. An AE can therefore be any unfavorable and unintended sign (including an abnormal laboratory finding, for example), symptom, or disease temporally associated with the use of investigational product, whether or not considered related to the investigational product. Adverse events can be spontaneously reported or elicited during open-ended questioning, examination, or evaluation of a subject. (In order to prevent reporting bias, subjects should not be questioned regarding the specific occurrence of one or more AEs.)

### 6.1 Serious Adverse Events

A *serious AE (SAE)* is any untoward medical occurrence that at any dose:

- results in death
  - is life-threatening (defined as an event in which the subject was at risk of death at the time of the event; it does not refer to an event which hypothetically might have caused death if it were more severe)
  - requires inpatient hospitalization or causes prolongation of existing hospitalization (see **NOTE** below)
  - results in persistent or significant disability/incapacity
  - is a congenital anomaly/birth defect
  - is an important medical event (defined as a medical event(s) that may not be immediately life-threatening or result in death or hospitalization but, based upon appropriate medical and scientific judgment, may jeopardize the subject or may require intervention [eg, medical, surgical] to prevent one of the other serious outcomes listed in the definition above.)
- Examples of such events include, but are not limited to, intensive treatment in an emergency room or at home for allergic bronchospasm; blood dyscrasias or convulsions that do not result in hospitalization.)

Suspected transmission of an infectious agent (eg, any organism, virus or infectious particle, pathogenic or non-pathogenic) via the study drug is an SAE. Although pregnancy, overdose and cancer are not always serious by regulatory definition, these events must be handled as SAEs for data transmission purposes (See Section 6.1.1 for reporting pregnancies).

**NOTE:** The following hospitalizations are not considered SAEs:

- a visit to the emergency room or other hospital department < 24 hours, that does not result in admission (unless considered "important medical event" or event life threatening)
- elective surgery, planned prior to signing consent
- admissions as per protocol for a planned medical/surgical procedure
- routine health assessment requiring admission for baseline/trending of health status (eg, routine colonoscopy)
- medical/surgical admission for purpose other than remedying ill health state and was

planned prior to entry into the study. Appropriate documentation is required in these cases – admission encountered for another life circumstance that carries no bearing on health status and requires no medical/surgical intervention (eg, lack of housing, economic inadequacy, care-giver respite, family circumstances, administrative).

### **6.1.1 Serious Adverse Event Collection and Reporting**

Following the subject's written consent to participate in the study, all SAEs, whether related or not related to study drug, must be collected, including those thought to be associated with protocol-specified procedures. SAEs (except those events considered secondary or related to disease progression) should be followed to resolution or stabilization. Follow-up is also required for SAEs that cause interruption or discontinuation of study drug, or those that are present at the end of study treatment as appropriate. The investigator should collect any SAE occurring after these time periods that is believed to be related to study drug or protocol-specified procedure. An SAE report should be completed for any event where doubt exists regarding its status of seriousness. If the investigator believes that an SAE is not related to study drug, but is potentially related to the conditions of the study (such as withdrawal of previous therapy, or a complication of a study procedure), the relationship should be specified in the narrative section of the SAE Report Form.

Any event that is both serious and unexpected must be reported to the FDA as soon as possible and, in no event, later than 7 days (death or life-threatening event) or 15 days (all other SAEs) after the investigator's or institutions initial receipt of the information. SAEs may be reportable to the FDA for both FDA-approved (post-market) drugs as well as investigational agents.

For an event to be reportable to the FDA, it must meet both of the following requirements as determined by the principal investigator of the study:

1. The event is possibly, probably or definitely related to the agent
2. The event is unexpected (i.e., not listed in the protocol, investigational brochure, or informed consent)

SAEs may be reportable to the FDA for both FDA-approved (post-market) drugs as well as investigational agents.

### **Reporting events for an APPROVED, POST-MARKET AGENT:**

The current MedWatch mandatory reporting form FDA 3500A can be found on the FDA website:

<http://www.fda.gov/Safety/MedWatch/HowToReport/DownloadForms/default.htm>

Use: [Form FDA 3500A - Mandatory Reporting](#)

Complete the *MedWatch* report and mail it to the appropriate address below:

**To report an event for an INVESTIGATIONAL AGENT under investigational new drug applications:**

Send a narrative of the event with circumstances, IND number, and why it is related and unexpected to the H. Lee Moffitt Cancer Center Regulatory Affairs IND Office.. A MedWatch report for the event would suffice. These events should not be reported or sent directly to the FDA by the study coordinator. The Regulatory Affairs IND Office at Moffitt Cancer Center will submit the reportable event as an IND safety report to the FDA on behalf of the principal investigator.

**If the principal investigator determines that the event could be possibly related and unexpected to *both the post-market agent and the investigational agent*, then the following should be done:**

- Submit the MedWatch report to the appropriate post-market address at the FDA as written above.
- Send the MedWatch report to regulatory affairs. The office will submit and IND safety report on the behalf of the principal investigator.

**Reporting SAEs to Novartis**

In addition to the reporting guidelines above, all SAEs, regardless of causality, should be reported to Novartis within 24 hours of becoming aware of the event. SAEs may be submitted in any format, using the fax cover sheets in Appendix 8.

If only limited information is initially available, follow-up reports are required. (Note: Follow-up SAE reports should include the same investigator term(s) initially reported.) If an ongoing SAE changes in its intensity or relationship to study drug or if new information becomes available, a follow-up SAE report should be sent within 24 hours to FDA using the same procedure used for transmitting the initial SAE report. All SAEs should be followed to resolution or stabilization.

## **6.2 Nonserious Adverse Events**

A *nonserious adverse event* is an AE not classified as serious.

### **6.2.1 Nonserious Adverse Event Collection and Reporting**

The collection of nonserious AE information should begin at initiation of study drug and continue through the day 90 follow-up visit with no new nonserious adverse events being reported past the end of treatment visit unless believed to be related to study drug. Post the EOT visit any ongoing AE's should be followed to resolution or stabilization, through the

day 90 follow-up, or reported as SAE's if they become serious (see Sections 6.1.1). Nonserious AE information should also be collected from the start of a placebo lead-in period or other observational period intended to establish a baseline status for the subjects. Follow-up is also required for nonserious AEs that cause interruption or discontinuation of study drug, or those that are present at the end of study treatment as appropriate. Completion of supplemental CRFs may be requested for AEs and/or laboratory abnormalities that are reported/identified during the course of the study.

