**C: Immune-related Adverse Experiences (irAEs) and DLT**

Definition of DLT in the context of irAEs will consider the incidence, severity, time of onset, duration and time to resolution for the specific irAE in the context of existing experience with ipilimumab. All Grade 3 or greater immune related AEs will be considered as potential DLTs. An independent DMC will be utilized to advise on aggregate safety data from this study and more specifically to review all Grade 3 or greater irAEs. Immune related AEs among patients treated with ipilimumab have clustered among skin, gastrointestinal, endocrine and liver-related events as follows:

Skin: alopecia, dry skin, hyperhidrosis, night sweats, pruritus, rash/desquamation, toxic epidermal necrolysis, urticaria, and vitiligo.

Gastrointestinal: abdominal discomfort or pain, anal ulcer, colitis (including ulcerative, haemorrhagic, ischaemic, and megacolon), constipation, cramping, diarrhea (including haemorrhagic), diverticulitis/diverticulum, duodenitis, dyspepsia, dysphagia, enteritis, esophagitis, gastritis (including erosive), gastrointestinal haemorrhage (including rectal), hematochezia, ileitis, ileus, intestinal obstruction, intestinal perforation (including small and large intestines), melena, nausea, pancreatitis, peritonitis, stomatitis (including aphthous), vomiting, vasculitis gastrointestinal.

Endocrine: adrenal insufficiency (including Addison's disease), glucose tolerance impaired, hyperthyroidism hypogonadism, hypophysitis/hypopituitarism (autoimmune), hypothyroidism, pituitary enlargement, thyroiditis (autoimmune).

Liver: hepatitis, jaundice

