**Table 5.12 During Treatment, Day 1 onward**

Study Cycle	Induction Cycle						Maintenance Cycle	End of Treatment	Follow-up	Notes
Cycle #	1				2		Each Cycle			
Day of Cycle 	1	5	22	35	1	22				
Safety Assessments										
Physical exam	X 		X		X	X	X	X	X	
Ophthalmology Exam	X									Baseline only
Vital Signs	X		X		X	X	X	X	X	
Weight	X		X		X	X	X	X	X	
PS	X 		X		X	X	X	X	X	
ECG	X 	X 			X		X	X		Triplicate 12-lead for Induction Cycle 1 Day 1 & Day 5; single 12-lead ECG otherwise
Chem Panel, CBC	X 		X		X	X	X	X	X	
PT/PTT	X 									
T4, TSH	X 		X		X	X	X			
Serum Preg	X 						X			
Urinalysis	X 				X		X			
SAE Monitoring	X		X		X	X	X	X	X	
Ipilimumab	X		X		X	X				
Panobinostat	X		X		X	X	X 			
Disease Assessment					X		X	X	X	
PD Blood	X		X		X	X	X	X		
Tumor bx				X 						

 All study visits may be scheduled +/- 3 days from planned visit date.

 These tests will not be repeated on Cycle 1 Day 1 of the initial treatment period if completed for screening less than 72 hours (3 days) before the first dose of the study drugs.

 Triplicate ECGs at least 5 minutes apart will be done pre-dose on C1 D1 & C1 D5.

 Biopsy to be done between Days 35 and 42.

 Panobinostat will continue to be administered thrice weekly during the maintenance cycles.

6. Patients will continue to be followed for PFS and OS.

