### **5.3 Safety Assessments**

All subjects who receive at least one dose of panobinostat and or Ipilimumab will be evaluated for safety parameters. Additionally, any occurrence of an SAE from time of consent until 90 days post discontinuation of study drug dosing will be documented. Safety will be evaluated for all treated subjects using the NCI CTCAE version 4.0. Safety assessments will be based on medical review of AE reports and the results of vital sign measurements, physical examinations and clinical laboratory tests. The incidence of AEs will be tabulated and reviewed for potential significance and clinical importance. The schedule or required visits, tests, procedures and assessments are described in the Procedural Outline Tables. In limited instances, scheduled evaluations can occur outside of this time frame but only within the windows noted. Please see the Procedural Outline Tables for a comprehensive list of assessments/procedures (Section 5.1). If the screening evaluation (physical exam, physical measurements, ECOG status and laboratory tests) is conducted within the 72 hour window of the first dose of panobinostat, then a single evaluation for these assessments may count for screening and pre-dose evaluation. If a subject has a delay in study drug administration for any reason, then assessments, laboratory tests and scans will be correspondingly delayed.

A screening 12-lead ECG will be performed to assess study eligibility. Additional 12-lead ECGs will be performed at a minimum at scheduled time points as indicated in Table 5.12. For all patients, a minimum of 3 sequential 12-lead ECGs, separated by at least 5 minutes, must be performed on cycle 1 day 1 prior to the first administration of oral panobinostat or within 72 hours prior to that day in order to get an accurate baseline QTcF calculation. Additionally, triplicate ECGs will be performed on cycle 1 day 5. The recommended dose modifications due to QTc interval prolongation are outlined in section 4.3.6.

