### 8.3.3 Safety Analyses

All recorded adverse events will be listed and tabulated by system organ class, preferred term, and dose and coded according to the most current version of MedDRA. The incidence of adverse events will be tabulated and reviewed for potential significance and clinical importance. Vital signs and clinical laboratory test results will be listed and summarized by and dose. Any significant physical examination findings and results of clinical laboratory tests will be listed. ECG listings will be evaluated by the investigator and abnormalities, if present, will be listed. A separate listing and summary of all immune-related adverse events (irAE) and inflammatory events regardless of causality (IERC) will be provided. In addition, the irAE rate will be estimated and a 90% confidence interval will be constructed for the irAE and the grade 3-4 GI irAE rate in each arm, based on the Clopper-Pearson method. The relationship between panobinostat exposure/dose and adverse event may be explored graphically and appropriate model may be fit.

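### After the end-of-treatment visit, unrelated new non-serious events go unrecorded, so the planned summary of inflammatory events regardless of causality is causality-filtered for that period

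*Combined protocol and SAP*

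**What the plan says.** Section 6.2.1 starts non-serious adverse event collection at first study drug and has it "continue through the day 90 follow-up visit". The same sentence then narrows what is collected after the EOT visit: "no new nonserious adverse events being reported past the end of treatment visit unless believed to be related to study drug". Events already under way are kept: "Post the EOT visit any ongoing AE's should be followed to resolution or stabilization", through Day 90.

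Serious events are treated differently. Under Section 5.3, "any occurrence of an SAE from time of consent until 90 days post discontinuation of study drug dosing will be documented", and Section 6.1.1 requires all of them, related or not.

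The planned output in Section 8.3.3 is: "A separate listing and summary of all immune-related adverse events (irAE) and inflammatory events regardless of causality (IERC) will be provided". The synopsis has the same commitment. Neither limits it to the on-treatment period.

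Section 4.3.3.1 C lists the organ systems in which immune-related adverse events (irAEs) cluster. Its endocrine entries include "hypophysitis/hypopituitarism (autoimmune), hypothyroidism, pituitary enlargement, thyroiditis (autoimmune"). In Table 5.12 the T4/TSH row is marked through the maintenance cycles and is blank at End of Treatment and Follow-up. The row "Chem Panel, CBC" is marked at both.

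**The concern.** An irAE, as Section 1.4.2.2 defines it, already requires an association with drug exposure and the exclusion or unlikelihood of other causes. The summary of inflammatory events regardless of causality (IERC) is the one planned safety output that does not depend on that judgement. In an open-label, single-site, first-in-human study of this combination, it is the natural guard against misattribution.

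The collection rule in 6.2.1 works against it. After EOT, a new non-serious inflammatory event that the investigator does not believe to be drug-related is not reported. No analysis can recover an event that was never recorded. Safety of the combination is the primary objective, and a reader of the final report would take the IERC table at its word for the whole observation period, including the 90 days after stopping.

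**Working it through.** The point sets collection rules against a planned output. The plan gives no figure to reproduce.

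**Step 1. Which events arising or continuing after EOT reach the IERC summary?**

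| Event | Recorded? | Source |
|---|---|---|
| Serious, any attribution | Yes, to 90 days | 5.3, 6.1.1 |
| Non-serious, ongoing at EOT | Yes, followed through Day 90 | 6.2.1 |
| New, non-serious, believed related (includes any event judged an irAE) | Yes | 6.2.1 with the definition in 1.4.2.2 |
| New, non-serious, inflammatory, judged unrelated | No under 6.2.1 | 6.2.1 |

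Only the last row is lost, and it is the row that separates an IERC summary from an irAE summary.

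**Step 2. Do other sections restore that row?** Section 5.3.1 requires laboratory abnormalities that the investigator finds clinically significant to go on the adverse event page. Section 6.3 asks for clinically significant results, and abnormalities leading to interruption, discontinuation or corrective therapy, to be captured as appropriate. Section 6.6 asks for significant worsening at interim or final examinations and other safety assessments to be recorded as a serious or non-serious event. None has a causality condition. After EOT they therefore point the opposite way from 6.2.1, and no section says which prevails. A site could follow either.

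**Step 3. Thyroid testing.** Reading Table 5.12 by column, T4/TSH is marked at Cycle 1 Days 1 and 22, Cycle 2 Days 1 and 22, and each maintenance cycle. It is blank at End of Treatment and Follow-up. Maintenance cycles last 84 days, so the last scheduled thyroid test can precede EOT by many weeks, and none is scheduled in the following 90 days. Physical examination and chemistry/CBC continue at both visits, so among these scheduled assessments the gap is specific to thyroid tests.

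**Step 4. Scale, by assumption only.** The documents give no rate of non-serious inflammatory events judged unrelated and no post-treatment onset rate. Suppose 0 to 3 subjects had their only such event in the lost row. The recorded incidence would be too low by m/n, where m is the number of subjects missed and n the number summarised:

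| m | n = 12 (largest planned size at one dose) | n = 36 (maximum total) |
|---|---|---|
| 0 | 0 | 0 |
| 1 | 1/12 = 8.3 points | 1/36 = 2.8 points |
| 2 | 2/12 = 16.7 points | 2/36 = 5.6 points |
| 3 | 3/12 = 25.0 points | 3/36 = 8.3 points |

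This shows how much one subject weighs at these sample sizes. It does not estimate the loss.

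**The case against.** The strongest reply is that nothing decisive rests on the missing events. Escalation and the MTD use drug-related dose-limiting toxicities within 84 days of starting therapy, and drug-related events pass the filter by definition. IERC is descriptive, with no comparator, test or confidence interval. All of this stands, and it limits the importance of the point.

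A reader might infer that the irAE rate and its 90% Clopper-Pearson interval are also biased low. The documents do not support that as a direct effect. An event judged an irAE is by definition associated with the drug, so 6.2.1 lets it through. The interval in 8.3.3 is for the irAE and grade 3-4 GI irAE rates, not for IERC. The irAE rate could suffer only indirectly, through misattribution or a thyroid event that no test picked up.

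It can also be said that 5.3.1, 6.3 and 6.6 would capture the events anyway. They may capture some. Because they contradict 6.2.1 and do not override it, loss is not certain, but neither is capture.

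Next, 8.3.3 tabulates recorded events and sets no IERC window, so one sentence there could remove the inconsistency without new data. That is a legitimate way out, provided the limit is stated.

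Finally, omitting T4/TSH at two visits contradicts no other section. Section 4.3.7.2 calls for close monitoring for endocrine signs, and the endocrine algorithm listed as Appendix 7 is not in the text available, so any testing it prescribes cannot be assessed. The thyroid item is therefore an inexpensive addition and not an inconsistency.

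**Conclusion.** The concern holds in a limited form. If 6.2.1 is followed as written, the IERC summary is causality-filtered for new non-serious events between EOT and Day 90, contrary to its own description. The conclusion assumes that IERC is meant to cover the whole collection period, since 8.3.3 and the synopsis set no shorter one. It is a modest defect in a secondary safety output, worth correcting because the correction is cheap and the data cannot be recovered later.

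The number of events lost cannot be derived from the documents. Two calculations might tempt a reader to put it at about two thirds, and neither measures it:

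- For a subject stopping at the 6-week assessment, 90/(42 + 90) = 68% of observed days fall after stopping. That is a share of calendar time, not of events. That subject also has a thyroid test scheduled at about the time of stopping, on Cycle 2 Day 1.
- Of the 50 endocrinopathies among 658 subjects in Section 1.4.2.2, 50 - 16 = 34 (68%) were below Grade 3. Those subjects received 10 mg/kg, whereas this trial gives 3 or 1 mg/kg and the same section describes irAEs as dose dependent. The cases were reported as irAEs, which would pass the filter. Endocrinopathy is broader than thyroid disease, and nothing in the documents shows that these cases were non-serious, found by laboratory test or of post-treatment onset.

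**What to change.** In 6.2.1, add one sentence: new non-serious inflammatory or immune-type events, defined by the organ list in 4.3.3.1 C, are collected through the Day 90 visit regardless of attribution. The relatedness filter can stay for other non-serious events. Reconcile 6.2.1 with 5.3.1, 6.3, 6.6 and 8.3.3 so that sites have one recording rule after EOT.

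If the sponsor prefers not to collect these events, 8.3.3 and the synopsis should state that, after EOT, IERC covers only drug-related new non-serious events plus all serious events.

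As a secondary change, mark T4/TSH in the End of Treatment and Follow-up columns of Table 5.12, so that thyroid events in the 90-day window can be detected.

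The cost is a few more adverse event entries and two assays per subject on blood already drawn. The design, sample size and escalation rules do not change.
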